# 9.3 Number of subjects

[figure not shown]
Approximately 160 subjects will be screened (approximately 96 for Part A and 64 for Part B) to achieve a total of 80 randomised and dosed subjects. The number may increase if additional dose cohorts need to be investigated and/or if recommended by the iSRC.

Part A: 48 subjects will be randomised and dosed in 6 cohorts (Cohorts A1 to A6, each of 8 subjects with 6 subjects receiving C106 and 2 subjects receiving placebo).

Part B: 32 subjects will be randomised and dosed in 4 cohorts (Cohorts B1 to B4, each of 8 subjects with 6 subjects receiving C106 and 2 subjects receiving placebo).

If indicated by emerging data and recommended by the iSRC, 2 cohorts (8+8 subjects) may be added to Part A and 1 cohort (8 subjects) may be added to Part B. In such cases, and to account for potential dropouts, additional subjects might be included in the trial.

For replacements of subjects who discontinue from the trial, see Section 9.8.

# 9.4 Inclusion criteria

For inclusion in the trial, subjects must fulfil the following criteria:

- 1. Willing and able to give written informed consent for participation in the trial. The signed informed consent should be obtained before initiation of any trial related procedures.
- 2. Healthy males and healthy females of non-childbearing potential aged 18-65 years inclusive.
- 3. Body Mass Index (BMI)  $\geq$  18.5 and  $\leq$  30.0 kg/m^2.
- 4. Clinically normal medical history, physical findings, vital signs, ECG, and laboratory values at the time of screening, as judged by the Investigator.
- 5. Women of non-childbearing potential, defined as pre-menopausal females who are sterilized (tubal ligation or permanent bilateral occlusion of fallopian tubes); or females who have undergone hysterectomy or bilateral oophorectomy; or post-menopausal defined as 12 months of amenorrhea (in questionable cases a blood sample with simultaneous detection of follicle stimulating hormone [FSH]  $\geq$  25 IU/L is confirmatory).

Male subjects must be willing to use condom or be vasectomised or practice sexual abstinence to prevent pregnancy and drug exposure of a partner and refrain from donating sperm from the date of dosing until 3 months after (last) dosing with the IMP. Their female partner of child-bearing potential must use highly effective contraceptive methods with a failure rate of < 1% to prevent pregnancy (combined [oestrogen and progestogen containing] hormonal contraception associated with inhibition of ovulation [oral, intravaginal, transdermal], progestogen-only hormonal contraception associated with inhibition of ovulation [oral, injectable, implantable], intrauterine device [IUD]or intrauterine hormone-releasing system [IUS]) from at least 4 weeks prior to dose to 3 months after last dose.

# 9.5 Exclusion criteria

Subjects must not enter the trial if any of the following exclusion criteria are fulfilled:

- 1. History of any clinically significant disease or disorder which, in the opinion of the Investigator, may either put the subject at risk because of participation in the trial, or influence the results or the subject's ability to participate in the trial.
- 2. Any clinically significant illness, medical/surgical procedure, or trauma within 4 weeks of the first administration of IMP.
- 3. Malignancy within the past 5 years except for in situ removal of basal cell carcinoma.
- 4. Any planned major surgery within the duration of the trial.
- 5. Any positive result on screening for serum hepatitis B surface antigen, hepatitis C antibody and Human Immunodeficiency Virus (HIV).

- 6. After 10 minutes supine rest at the time of screening, any vital signs values outside the following ranges:
  - Systolic blood pressure <90 or >140 mmHg, or
  - Diastolic blood pressure <50 or >90 mmHg, or
  - Pulse <40 or >90 bpm
- 7. Prolonged QTcF (>450 ms), PR interval < 120 ms or > 240 ms, QRS>115 ms, clinically significant cardiac arrhythmias or any clinically significant abnormalities in the resting ECG at the time of screening, as judged by the Investigator.
- 8. History of severe allergy/hypersensitivity or ongoing allergy/hypersensitivity, as judged by the Investigator, or history of hypersensitivity to drugs with a similar chemical structure or class to C106.
- 9. Regular use of any prescribed or non-prescribed medication including antacids, analgesics, herbal remedies, vitamins and minerals within 2 weeks prior to the (first) administration of IMP, at the discretion of the Investigator.
- 10. Planned treatment or treatment with another investigational drug within 3 months prior to Day -1. Subjects consented and screened but not dosed in previous clinical trials are not excluded.
- 11. Current smokers or users of nicotine products. Irregular use of nicotine (*e.g.*, smoking, snuffing, chewing tobacco) less than three times per week is allowed before screening visit.
- 12. Positive screen for drugs of abuse or alcohol at screening or on admission to the unit prior to administration of the IMP.
- 13. History of alcohol abuse or excessive intake of alcohol, as judged by the Investigator.
- 14. Presence or history of drug abuse, as judged by the Investigator.
- 15. History of, or current use of, anabolic steroids.
- 16. Excessive caffeine consumption defined by a daily intake of >5 cups of caffeine containing beverages.
- 17. Plasma donation within one month of screening or blood donation (or corresponding blood loss) during the three months prior to screening.
- 18. Investigator considers the subject unlikely to comply with trial procedures, restrictions, and requirements.

# 9.6 Restrictions during the trial period

## 9.6.1 *General restrictions*

The subjects must be willing to comply to the below restrictions during the entire trial duration i.e., from screening to the end-of-trial visit (or longer if specified).

• Contraception Requirements: The male volunteers are expected to use condom to prevent pregnancy and drug exposure of a partners and refrain from donating sperm from the date of dosing until 3 months after last dosing of the IMP. Fertile female partners are expected to use highly effective contraceptive methods with a failure rate of

< 1% to prevent pregnancy from at least 4 weeks prior to dose to 3 months after last dose (for details regarding contraceptive methods, refer to inclusion criterion No 5).

• Meals and Dietary Restrictions: Standardised meals will be served on Day -1 and Day 1 in Part A (SAD) and on Day -1, Day 1, Day 7 and Day 8 in Part B (MAD). Nonstandardised meals will be served on the other days. Lunch will be served at least 4 hours post-dose. Snack, dinner, and optional evening snack will be served approximately 7-, 9- and 11-hours post-dose, respectively.

For details on IMP administration in fasted and fed state, refer to Section 10.5.1.

Standardised meals: A menu option decided by CTC. The meal selection is standardised in the sense that the nutritional content of the meals should be similar at each time point of each treatment day.

- Fasting: In Part A (SAD), the subjects should be fasting overnight (10 hours) before Day 1 and until 4 hours post-dose (except in the fed cohort). In Part B (MAD), subjects must fast from 2 hours prior to each IMP administration until 1-hour post-dose. Water is allowed *ad libitum* at the clinic except 1 hour before dose and 1 hour after dose. The IMP will be taken with water (approximately 240 mL, including the volume of the IMP). Subjects participating in Part B, cohort B4 must fast for at least 4 hours prior to the EndoPAT assessment until end of assessment.
- Sun protection: Protection from the sun is required from each C106 administration until 3 days post dose in Part A and from the first until 3 days after the last C106 administration in Part B. Study subjects are required to follow the recommendations given by Centres for Disease Control and Prevention (CDC, see [45]):
  - Stay in the shade, especially during sun peak hours of 10 AM to 4 PM.
  - Wear clothing that covers arms and legs.
  - Use a hat or cap that shades the face, head, ears, and neck.
  - Wear sunglasses that block both ultraviolet A (UVA) and ultraviolet B (UVB) rays
  - Proper use of a broad-spectrum sunscreen with a sun protection factor (SPF) of 15 or higher.
  - Abstain from use of tanning beds.
- Alcohol: Consumption of alcohol is not allowed within 48 hours prior to the screening visit and all subsequent visits to the clinic including the end-of-trial visit of each part. In addition, consumption of alcohol is disallowed during all visits to the clinic.
- Drugs of abuse: Use of drugs of abuse is not allowed within 48 hours prior to the screening visit and during the entire trial duration *i.e.*, from screening to the end-of-trial visit.
- Coffee: Consumption of up to 5 cups of coffee per day will be allowed from screening to the end-of-trial visit of each part.
- Xanthine or taurine containing products/beverages: Energy drinks (*e.g.*, Red Bull) are not allowed from screening to the end-of-trial visit of each part.
- Nicotine: Smoking or use of nicotine-containing products is not allowed from screening to the end-of-trial visit of each part.

- Grapefruit and grapefruit containing products: Consumption of grapefruit and/or grapefruit containing products, Seville oranges is not allowed from screening to the end-of-trial visit of each part.
- Exercise: The subjects must refrain from strenuous exercise for 72 hours before and during any visit to the clinic.
- Blood donation: The subjects must not donate blood or plasma during the trial until 3 months after the final medical examination at the end-of-trial visit of each part.
- Participation in other clinical trials: The subjects are not allowed to participate in any other interventional clinical trial from screening to the end-of-trial visit of each part.
- Trial intervention and observation periods: The subjects are not allowed to leave the research clinic during residential stays at the research clinic (Visit 2 in both Part A and Part B), unless authorised by the trial personnel.

## 9.6.2 **Prior and concomitant therapy**

## Prohibited medication

Regular use of any prescribed or non-prescribed medication including antacids, analgesics, herbal remedies, vitamin supplements and minerals from 2 weeks prior to the (first) administration of IMP at the discretion of the investigator.

Any use of prescribed or non-prescribed medication including antacids, analgesics, herbal remedies, vitamin supplements and minerals from the (first) administration of IMP until the end-of trial visit of each part is not allowed except as detailed below.

Allowed medication

- Paracetamol in doses up to 2000 mg/day for a maximum of 3 consecutive days. If this amount of paracetamol is not sufficient for treatment of the subjects, withdrawal should be considered.
- Nasal decongestants without cortisone, antihistamine or anticholinergics for a maximum of 10 days.
- Hormone replacement therapy.

Other medications considered necessary for the subject's safety and wellbeing may be given at the discretion of the Investigator during the residential period. Following consultation with the Sponsor, the Investigator will determine whether or not the subject should continue in the trial.

## 9.7 Screen failures

Screen failures are defined as subjects who consent to participate in the clinical trial but do not fulfil all eligibility criteria and are not subsequently randomised in the trial. A minimal set of screen failure information is required to ensure transparent reporting of screen failure subjects. Minimal information includes documentation of signed and dated informed consent form (ICF) and reason(s) for screening failure.

Re-screening can be performed if any of the following were reasons for screening failure or non-randomisation (as judged by the Investigator):

- Practical reasons.
- Non-significant medical conditions (*e.g.*, influenza, nasopharyngitis).
- Reserve subject in previous cohort.
- Plasma or blood donation outside allowed time windows.

For subjects who are re-screened, a new screening number will be assigned and a new, signed ICF will be collected.

# 9.8 Subject withdrawal

# 9.8.1 General withdrawal criteria

Subjects are free to discontinue their participation in the trial at any time and for whatever reason without affecting their right to an appropriate follow-up investigation or their future care. If possible, the reason for withdrawal of consent should be documented.

Subjects may be withdrawn from the trial at any time at the discretion of the Investigator.

Reasons for withdrawal include:

- Subject decision
- Severe non-compliance to trial protocol procedures, as judged by the Investigator and/or Sponsor
- Subject is lost to follow-up
- Significant AEs posing a risk for the subject, as judged by the Investigator and/or Sponsor
- Withdrawal of informed consent to the use of biological samples
- Pregnancy
- Death
- Meeting of an exclusion criterion during the trial, which, in the opinion of the Investigator, may pose a risk for the subject
- Use of prohibited medication

## 9.8.2 *QTc withdrawal criteria*

A subject meeting the criteria below will be withdrawn from the trial. The same QT correction formula will be used to determine discontinuation throughout the trial.

- QTcF > 500 msec
- Change from baseline: QTcF > 60 ms

Withdrawal decisions will be based on an average QTc value of triplicate ECGs. If an ECG demonstrated a prolonged QT interval, two more ECGs will be obtained over a brief period

and the averaged QTc values of the three ECGs used to determine whether the subject should be discontinued from the trial.

# 9.8.3 *Liver chemistry withdrawal criteria*

Liver chemistry threshold stopping criteria have been designed to assure subject safety and to evaluate liver event aetiology. Trial treatment will be stopped for the individual subject if any of the following liver chemistry stopping criteria, defined in the FDA Guidance on Drug-Induced Liver Injury [46], is met:

• Alanine aminotransferase (ALT) 3 x Upper Limit of Normal (ULN) and total bilirubin  $\geq 2xULN$  (>35% direct bilirubin); or ALT 3xULN and INR > 1.5.

NOTE: plasma bilirubin fractionation will be performed.

- ALT 5xULN.
- ALT 3xULN if associated with symptoms (new or worsening) believed to be related to hepatitis (such as fatigue, nausea, vomiting, right upper quadrant pain or tenderness or jaundice) or believed to be related to hypersensitivity (such as fever, rash, or eosinophilia).

# 9.8.4 *Procedures for discontinuation of a subject from the trial*

A subject who prematurely discontinues participation in the trial will always be asked about the reason(s) for discontinuation and the presence of any AEs. If a subject withdraws consent, the Investigator must ask the subject if he/she is willing, as soon as possible, to be assessed according to the procedures scheduled for the end-of-trial visit in each part. Any ongoing AEs will be followed as described in Section 11.3.1.15.

The primary reason for discontinuation/early withdrawal must be specified in the eCRF and final drug accountability must be performed. If the primary reason is an AE, the AE must be specified.

# 9.8.5 Subject replacement

Subjects who are prematurely withdrawn from the trial for any reason except the occurrence of AEs assessed as possibly or probably related to trial treatment may be replaced during the course of the trial.

Part A (SAD): subjects who are randomised but not dosed will be replaced. Subjects who are dosed will not be replaced.

In the event of dropouts in the fed cohort, subjects may be replaced to guarantee a full cohort size for the food-interaction part of the trial. Any replacers will receive active treatment both in the fasted and fed state.

Part B (MAD): Subjects who are randomised but not dosed will be replaced. Subjects who were prematurely withdrawn from the trial for any reason except the occurrence of AEs assessed at least possibly related to the IMP may be replaced.

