# 8.1.1.1 Food interaction

One dose cohort (planned to be cohort A4) will be selected to investigate any potential food interaction. The predicted maximum exposure (taking into account a possible food interaction effect on the exposure) of the chosen dose level will not exceed the exposure tolerated in previously evaluated cohorts.

Subjects in the selected cohort will return to the clinic after a wash-out period of at least 5 half-lives (as determined by evaluation of PK data) to receive a second dose of C106 or placebo under fed conditions. In case of dropouts at the selected dose level, subjects may be replaced to guarantee a full cohort size for the food-interaction part of the trial (if considered necessary). Any replacers will receive active treatment. The assessments during fed conditions will be the same as during fasting conditions except that the subjects will consume an FDA recommended high-fat, high calorie breakfast 30 minutes prior to IMP administration as detailed in Section 10.5.1 and no screening visit will be conducted. Potential replacement subjects will come for a screening visit and perform one fasting cohort and one fed cohort.

The schedule of events for Part A is shown in Table 8.1-1 and detailed for Visit 2 in Table 8.1-2.

Trial assessments are described in Section 11.

Table 8.1-1 Schedule Visit Assessment	Refer to CTP section:	Screening		nterven rvation		d	Follow-up/End-of-trial		
		Visit 1 Day -28 to Day -1	Visit 2 			Visit 3			
			Admission Day -1	Day 1	Day 2	Day 3	Day 7 (±2) 		
Informed Consent	14.3	Х							
Inclusion/exclusion criteria	9.4, 9.5	Х		Х					
Demographics	11.2	Х							
Medical/surgical history	11.2.5	Х							
HIV, hepatitis B and C	11.2.7	Х							
Alcohol test	11.2.9	Х	Х						
Weight/height (BMI)	11.2.4	Х							
Serum FSH 	11.3.5	Х							
Urine Drug Screen 	11.2.8	Х	Х						
Physical Examination	11.3.2	Х		X 			Х		
Clinical Laboratory Profile 	11.3.5	Х	Х		X	X	Х		
Safety urine sampling	11.3.5	Х	Х		Х	X	Х		
Urinalysis (dipstick)	11.3.5	Х	Х				Х		
Vital Signs 	11.3.4	Х	Х	Х	X	X	Х		
12-lead safety ECG	11.3.2	Х		Х	X	X	Х		
Telemetry	11.3.3			X9					
Randomisation				Х					
IMP administration	10.5			X 					
Cardiodynamic ECG 	11.5.3			Х	X				
PK blood sampling	11.4.1			Х	Х	Х			
PK urine sampling	11.4.2			Х	X	X			
Breakfast					X	Х			
High-fat breakfast 	10.5.1			X 					

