# 9.9 Randomisation

On Day 1 of each part, subjects in each cohort will be randomised to receive either C106 (n=6) or placebo (n=2). Subjects will be randomised in 2 blocks. The first 2 subjects in a cohort will be randomised to C106 (n=1) or placebo (n=1). The next subjects will be randomised in a 5:1 ratio to receive C106 (n=5) or placebo (n=1). A computer-generated randomisation list will be created using SAS Proc Plan, SAS Version 9.4. The randomisation list will contain subject number and treatment and will be kept by the randomiser in a sealed envelope until database lock. A copy of the randomisation list will be kept by an unblinded IMP preparation staff member at the site.

Sealed individual, treatment code envelopes will be kept at the clinic and at CTC's Pharmacovigilance department (CTC PV) in locked and restricted areas if needed for emergency unblinding.

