# 9.10 Blinding

This is a double-blind trial, and the allocation of treatments will not be disclosed until clean file has been declared and the database has been locked.

The IMP, *i.e.*, the C106 and the placebo oral solutions, are identical in appearance. Both solutions are colourless to yellow. Hence, it is expected that the subjects, Investigator and other site personnel will remain unaware of treatment allocation.

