# **10.5** Treatment administration

## 10.5.1 Treatment administration Part A

Subjects in Part A (SAD) will be administered a single oral dose of either C106 or placebo as randomised. The proposed doses are 5, 30, 60, 180, 240 and 300 mg C106.

Subjects who participate in the food interaction part will be administered a second single dose of either C106 or placebo. Any replacers in the food interaction part will receive C106 and will participate in both a fasting and a fed period.

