#### 17.3 Analysis data sets

#### 17.3.1 Full analysis set

The Full Analysis Set (FAS) will consist of all subjects who have been randomised and received at least one dose of IMP and who has at least one post-baseline assessment of data. The FAS will be used for all safety and PD evaluations.

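### Food-interaction replacers get C106 by rule, so as worded they fall outside the only safety analysis set, and site staff who know their status can infer the treatment

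*Combined protocol and SAP*

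**What the plan says.** The rule for replacers appears in four places and is consistent. Section 9.8.5 has "Any replacers will receive active treatment both in the fasted and fed state". Section 8.1.1.1 has "Any replacers will receive active treatment", and the Synopsis paragraph on food interaction agrees. Section 10.5.1 has "Any replacers in the food interaction part will receive C106 and will participate in both a fasting and a fed period". Replacement is optional: Section 9.8.5 permits it when subjects drop out of this cohort, so that the food comparison keeps its planned size.

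Three other sections bear on this:

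- **Section 9.9, Randomisation.** Each cohort of 8 is allocated in two blocks, a sentinel pair at 1:1 and then six subjects at 5:1. Replacers are not mentioned.
- **Section 9.10, Blinding.** The trial is double-blind, and "the allocation of treatments will not be disclosed until clean file has been declared and the database has been locked". No exception is made for replacers.
- **Section 17.3, Analysis data sets.** The FAS "will consist of all subjects who have been randomised and received at least one dose of IMP" and have some post-baseline data. It serves all safety and PD evaluations. The pharmacokinetic set (PKAS, Section 17.3.2) asks for dosing and plasma data, without protocol deviations or adverse events that affect the PK. It does not ask for randomisation.

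**The concern.** A subject whose treatment is fixed in advance has not been randomised. If the FAS definition is applied as written, a replacer who takes C106 twice in a first-in-human trial is left out of the summaries that address the primary objective. If the replacer is instead added informally, subjects whose treatment the site can infer are pooled with blinded subjects and not marked as such.

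Knowledge of treatment matters here because much of the safety evidence is judgement. The Investigator decides whether an adverse event is related (Section 11.3.1.8) and whether ECG, vital sign and laboratory abnormalities are clinically significant (Sections 11.3.2, 11.3.4 and 11.3.5). The adverse event stopping rules in Table 8.3-3 depend on relatedness, and the Principal Investigator or a delegate is one of the two voting members of the safety review committee (Section 8.3.6).

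**Working it through.** **1. The plan's own count.** Section 9.3 plans 6 cohorts × 8 = 48 subjects in Part A and 4 × 8 = 32 in Part B, and 48 + 32 = 80, as stated. Replacers are not part of this count. No sample size formula applies.

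**2. Is a replacer randomised?** From Section 9.9, the probability of receiving C106 is:

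- sentinel pair: 1/2 = 50%
- remaining six: 5/6 = 83%
- cohort overall: 6/8 = 75%
- food-interaction replacer (Sections 8.1.1.1, 9.8.5, 10.5.1): 1, that is 100%

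An allocation with probability 1 has no random element. Sections 10.2 and 10.4 have IMP labelled and prepared from the randomisation schedule or list, and they describe no separate route for a replacer.

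**3. Which analysis sets admit a replacer?**

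- FAS: randomised? No. Dosed? Yes. Post-baseline data? Yes, normally. Literal result: out.
- PKAS: dosed? Yes. Plasma data? Yes, normally. Literal result: in.

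The PKAS would then contain subjects who are not in the FAS.

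**4. Size.** The documents give no number of replacers, so let r be an assumed number. Cohort A4 has 6 subjects on C106. Those who drop out after the fasted dose stay in the FAS if they have a post-baseline assessment. With no other losses, actively dosed subjects in the cohort number 6 + r, of whom r fall outside the FAS:

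- r = 0: 0/6 = 0%
- r = 1: 1/7 = 14.3%
- r = 2: 2/8 = 25%
- r = 3: 3/9 = 33.3%
- r = 6: 6/12 = 50%

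Across Part A, 6 × 6 = 36 subjects are planned on C106, so the shares are 1/37 = 2.7% for r = 1 and 2/38 = 5.3% for r = 2.

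**5. Blinding.** Known replacer status together with the protocol text gives the treatment with certainty. The identical appearance of the two solutions (Section 9.10) does not help, because the information comes from the rule and not from the product.

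**6. A related conflict.** The Synopsis brings back for the fed period the subjects who had C106 when fasted. Section 8.1.1.1 brings back the subjects of the selected cohort, and both it and Section 10.5.1 allow the second dose to be C106 or placebo. These passages cannot all hold. Which one applies determines whether being recalled reveals the allocation.

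**The case against.** The strongest reply is that the rule serves its purpose. Replacement exists to complete a within-subject PK comparison, C106 concentrations are not biased by knowing the treatment, and the PKAS does not require randomisation. That stands: the food-effect estimate is not affected. It is also why I would not ask that a replacer take over the allocation of the subject replaced. A placebo replacer would add no food-effect PK.

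A second reply is that replacers follow Table 8.1-1, which lists randomisation on Day 1, and might be given a formal number and counted in the FAS. No passage says so, and Section 9.9 has no slot for them, so this leaves an ambiguity and does not settle it. Section 17 refers to a more detailed SAP, which could also settle it but is not in the text available. Section 17.5.1 lists all adverse event data by subject, and escalation decisions use all available safety data, so the likely gap is in the summary tables.

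A reader might infer more than the documents support:

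- **That exposed subjects have already been lost.** Table 8.3-2 shows 6 subjects with PK data at 180 mg in cohort A4. The documents do not say whether the fed period has taken place or whether any replacer was dosed.
- **That the replacer also knows the treatment.** This depends on the subject information, which is not available. The contradiction with Section 9.10 needs only the site's knowledge.
- **That replacing a placebo dropout turns the cohort from 6:2 into 7:1.** A placebo subject dosed fasted stays in the FAS, given a post-baseline assessment, so the FAS remains 6:2 as worded. If all dosed subjects are counted, the fasted period is 7:2. The 7:1 split could arise only in the fed period, and only if placebo subjects return, which the Synopsis does not provide for. Any probability that a dropout was on placebo rests on the same unresolved conflict.
- **That the replacer rule is what leaks allocation in this cohort.** On the Synopsis reading, recall for the fed period itself discloses treatment, with or without replacers.

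**Conclusion.** The point holds as a defect of definition. As worded, food-interaction replacers are non-randomised, lie outside the only set used for safety, can enter the PKAS, and are not effectively blinded to site staff who know their status. The size is conditional: nil without replacers, 14% of the actively dosed subjects in that cohort with one, and 25% with two. These shares assume a literal reading of the FAS, 6 subjects dosed with C106 in the selected cohort, and no other losses. Safety analysis is descriptive, so no formal test is affected. The consequence is incomplete or unmarked safety summaries for one cohort. That is worth correcting because safety is the primary objective and the correction is cheap.

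**What to change.** 1. In Section 17.3.1, and in the SAP, define the safety set as every subject who took IMP at least once, summarised by treatment received.
2. In Sections 9.9 and 9.10, state that food-interaction replacers are not randomised and that their treatment is known to the site.
3. Flag replacers in the adverse event tables and listings, so that judgements made with knowledge of treatment can be told apart from blinded ones.
4. Reconcile the Synopsis with Sections 8.1.1.1 and 10.5.1 on who returns for the fed period and on what treatment.

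The cost is wording in the protocol and SAP and one indicator variable. The number of subjects and the assessments do not change. Item 1 has no evident downside and can be in place before database lock, when Section 17 requires the SAP to be signed. Items 2 and 3 keep the rule on replacers as it is and make its consequences explicit.
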